10.7. Group Allocations

Both right (quadrant 1 and 4) and left (quadrant 2 and 3) halves of all 14 participants, split mouth design will be assigned randomly to one of two treatment modalities via computer generated random sequence done by supervisor. A simple randomisation method will be employed to assign 14 participants into two groups (Group 1 and Group 2 corresponding to right halves: test and left halves: control or right halves: control and left halves: test) alternatively. A series of random numbers will be generated using the Numbers RAND() formula, done by supervisor, [name]. The RAND() function in Numbers produces uniformly distributed random numbers between 0 and 1. Fourteen unique random numbers will be generated, one for each participant in the study. The assigned random numbers will be sorted in ascending order from smallest to largest. This

step ensured that the patients will be arranged in a random sequence. Patients will then be assigned to two groups (Group 1 and Group 2) alternatively, starting with Group 1. This process will start with Group 1 and continue with Group 2, then back to Group 1, and so forth, until all patients were assigned to a specific group. The treatment allocation cards were sealed in envelopes until the clinical procedure.

The random allocations sequences will be concealed in a sequential sealed opaque envelope by [name] and will only be opened on the day of intervention's applications. Subgingival applications of either control drops and *Lactobacillus reuteri* probiotic drops will be done by [name].

Groups	Treatment
Control Halves	
On day 0, baseline record will be taken. Then, subjects will receive motivation and oral hygiene instructions on standard effective oral hygiene practice which include tooth brushing, flossing, interdental brush usage and single tufted brush, followed by professional mechanical plaque removal (PMPR) and root surface debridement (RSD). Following this, the control quadrants will be receiving application of the control drops (sterile distilled water) immediately after RSD together with post-operative instructions. Oral hygiene kit will also be given. ([name])
 
Reapplications of control drops together with oral hygiene review visit will be done on day 7, 14, 21 and 28 days after the first subgingival control applications. ([name])
 
Follow up visit for assessment of BoP, PPD, CAL, PI and GI will be done at 3 months interval from the baseline. ([name])

Test Halves	
On day 0, baseline records will be taken. Then, subjects will receive motivation and oral hygiene instructions on standard effective oral hygiene practise which include tooth brushing, flossing, interdental brush usage and single tufted brush, followed by professional mechanical plaque removal (PMPR) and root surface debridement (RSD). Following this, the control quadrants will be receiving application of the test drops (Lactobacillus reuteri probiotic) immediately after RSD together with post-operative instructions. Oral hygiene kit will also be given. ([name])
 
Reapplications of test drops together with oral hygiene review visit will be done on day 7, 14, 21 and 28 days after the first subgingival control applications. ([name])
 
Follow up visit for assessment of BoP, PPD, CAL, PI and GI will be done at 3 months interval from the baseline. ([name])

-------------	--

Treatment for root surface debridement will be done under local anaesthesia on all subjects by single clinician, [name] for all 14 patients at Day 0, right after baseline parameters recorded and oral hygiene instructions and motivations given. All patients will be recall back after 3 months to assess the clinical parameters (BoP, PPD, CAL, PI and GI) by [name].

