10.1. Preparation of *Lactobacillus Reuteri* Probiotic

For this study, we will be using the BioGaia probiotic drops containing a minimum of 100 million live patented lactic acid bacterium *Limosilactobacillus reuteri* (*L. reuteri* DSM 17938) per dose which is 'HALAL' certified and is fit for consumption by human and also recommended for oral intake.

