10.3. Subjects

All periodontitis patients who attended MAHSA Dental Clinic are eligible for this study. Screening will be done by main examiner and 14 subjects who fulfil the inclusion and exclusion criteria will be recruited with consent. Dental Panoramic Tomogram (DPT) will be then taken to confirm the presence of bone loss with expert periodontist and alginate impression will also be taken to fabricate acrylic stents with reference marks for both arches on each patient for pocket localisation to determine exact measurement sites in every visits.

Inclusion Criteria

• Periodontitis patient aged between 18 and 65 years.• Periodontitis patient with controlled type 2 diabetes mellitus ($HbA1c < 7\%$).• Periodontitis patient present with Stage II, Stage III and Stage IV periodontitis, based on New 2017 Classification of Periodontal and Peri-Implant Disease and Conditions (Papapanou et al., 2018) with at least 20 teeth present.• No history of antibiotics or probiotics for any purpose and periodontal therapy within the past 6 months.

Exclusion Criteria

- Involvement in another clinical trial.
- Pregnancy or lactation.
- Smoker/ alcoholic.
- Completely edentulous individuals.
- Individuals with a history of systemic diseases, such as acquired immune deficiency syndrome, cardiovascular disorders, hepatic diseases (including hepatitis b and c) and renal diseases.
- Individuals with overlapping teeth.
- Individuals that reported to have undergone periodontal therapy within the past 6 months.
- Individuals that reported to have used antibiotics, probiotics, non-steroidal anti-inflammatory drugs and/ or steroid use within the past 6 months.
- Individuals with physical limitation that might hinder proper oral hygiene procedures.

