day of applications. Post-operative instructions will be given after the applications to all subjects. Each subject will also be given the same oral hygiene kit containing soft bristle toothbrush, single tufted brush, interdental brush, fluoridated toothpaste and dental floss. The applications will be repeated again in both groups after initial applications on every 7, 14, 21 and 28 days (Sufaru et al., 2022), all by student [name].

Follow up visit to evaluate all clinical parameters will be done on every subject, at three months (Segelnick & Weinberg, 2006) after treatment (RSD) by main examiner, [name].

[figure not shown]
10.5. *Lactobacillus Reuteri* Probiotic Applications

The subgingival applications of control (sterilised distilled water) and test (*Lactobacillus reuteri* probiotic) drops will be done after RSD on all pockets of $\geq 5\text{mm}$ (Matesanz-Pérez et al., 2013; Passariello et al., 2012), on each groups, in the same day after RSD completion. The subgingival applications will be done using 1mL disposable syringe attached with blunt soft Intra Vascular cannula tip (22 Gauge). Isolation will be done using cotton roll and saliva suction will be used to avoid saliva contaminations as possible. The control/ *Lactobacillus reuteri* probiotic drops will be introduced into the pocket, until overfill is observed at the gingival margin (Griffiths et al., 2000; Unsal et al., 1994). Subjects will then be instructed not to eat, drink or rinse for at least 30 minutes. Only tooth brushing will be instructed to subject and to avoid sticky food and chewing hardly on the applied area. The control and *Lactobacillus reuteri* probiotic drops applications will be repeated every 7, 14, 21, and 28 days (Sufaru et al., 2022), following the same duration procedure. Oral hygiene instruction will also be re-emphasised on each

visit. Follow up visit for assessment of clinical parameters (BoP, PPD, CAL, PI and GI) will be done at 3 months interval for both groups.

Picture showing example of acrylic stent with marking. *Journal of Indian Society of Periodontology - Vol 13, Issue 2*

Picture showing a 1mL disposable syringe attached with blunt soft flexible tip (0.25mm) which will be used for subgingival applications of control and *Lactobacillus reuteri* probiotic drops.

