10.9. Study Flow Chart

11. Statistical Analysis

All data will be collected in numerical form and will be analysed using the IBM SPSS Statistics Version 26.0 software. Histogram plot of data will be first used to check for normality of data distribution. Then, either Independent t-Test or Mann-Whitney Test will be used to compare data between two groups. The variables will be presented as mean and standard deviation for parametric test or median and interquartile range for non-parametric test. Significant level will be set at p-value $p < 0.05$. Meanwhile data within groups to evaluates statistically significant changes from baseline to follow up visits will be analysed either using Paired t-Test or Wilcoxon Signed Ranked Test.

Parameter	Visit	Control group	Test group	p-Value
BoP	Baseline			
	3 months			
PPD (mm)	Baseline			
	3 months			
CAL (mm)	Baseline			
	3 months			
PI	Baseline			
	3 months			
GI	Baseline			
	3 months			

Clinical Parameters for Groups 1 and 2 (mean \pm SD or median (IQR)) at different time intervals

(*denotes statistically significant difference, $p < 0.05$)

12. Budget

	Quantity	Cost/ Unit	Total Cost
Disposable syringe (1ml) (100's/ box)	1	RM 50.00	RM 50.00
Flexible tip (0.25mm) (100's/ box)	1	RM 200.00	RM 200.00
Gracey curettes	28	RM 209.25	RM 5859.00
Sharpening kit	1	RM 2442.00	RM 2442.00
Small cassette	3	RM 592.50	RM 1777.50
Lactobacillus reuteri probiotic	20	RM 134.50	RM 2690.00
Acrylic stents	20	RM 200.00	RM 4000.00
Oral hygiene kit	20	RM 100.00	RM 2000.00
		T O T A L COST	RM 19,018.50

13. Gantt Chart

	2023	2024				2025				2026			
	NOV- DEC	JAN- MAR	APR- JUN	JUL- SEP	OCT- DEC	JAN- MAR	APR- JUN	JUL- SEP	OCT- DEC	JAN- MAR	APR- JUN	JUL- SEP	OCT- DEC
Drafting proposal													
Defence of research proposal (DRP)													
Ethics application													
Data collection preparation													
Data collection													
Thesis write-up													
Submission research paper													
Thesis submission for viva													
Research sends for publication													

14. References

- Chandran, Arunah. (2020). National Diabetes Registry Report, 2013-2019. Ministry of Health Malaysia. https://www.moh.gov.my/moh/resources/Penerbitan/Rujukan/NCD/Diabetes/National_Diabetes_Registry_Report_2013-2019_26082021.pdf

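### As far as the available text shows, no visit records adverse events or drugs taken after day 0, so the trial could not describe tolerability

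*Combined protocol and SAP*

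**What the plan says.** Sections 10.5 and 10.7 place drops in pockets of 5 mm or more on day 0, straight after root surface debridement, and repeat this on four later days. For the test halves, 10.7 states: "Reapplications of test drops together with oral hygiene review visit will be done on day 7, 14, 21 and 28 days". The control-half entry is parallel. Section 10.5 has the operator fill each pocket "until overfill is observed at the gingival margin" and adds: "Oral hygiene instruction will also be re-emphasised on each" visit. Post-operative instructions go to every patient, but their content is not given.

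For the last visit, 10.7 states: "Follow up visit for assessment of BoP, PPD, CAL, PI and GI will be done at 3 months interval from the baseline". Section 10.6 lists the same five indices as the parameters to be recorded. The table shell in Section 11 has rows for those five only, at baseline and 3 months.

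Drug use appears in 10.3 as an entry exclusion: "Individuals that reported to have used antibiotics, probiotics, non-steroidal anti-inflammatory drugs and/ or steroid use within the past 6 months". No section that we could read asks about these drugs after entry.

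Section 10.1 describes the product as "fit for consumption by human and also recommended for oral intake". Section 8 says that clinical use of this probiotic in type 2 diabetes has not been studied. Sections 6.1 and 6.2 set effectiveness objectives only.

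**The concern.** A live bacterial product is put by cannula into recently debrided deep pockets, up to five times, in patients with diabetes. The operator looks at the treated margins each time, yet the visible text does not require anyone to ask about symptoms or write down what is seen. An abscess, suppuration, pain or fever that clears before month 3 would leave no trace in an index charted at month 3. Even an event still present then would appear only as an index score, not as an event.

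The plan's own reasoning makes this matter. Section 9 gives the side effects of chemical antimicrobials as a reason for turning to probiotics. A trial with that motive should be able to say what unwanted effects it saw. Likewise, 10.3 treats four drug classes as important enough to exclude for six months before entry, and the plan then stops tracking them. What is not written down at the visit is not reliably available at analysis.

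**Working it through.** **Plan's own figure.** Section 10.2 takes a minimum of 12 patients and adds 10% for dropout: 12 + 12 × 0.10 = 13.2, rounded up to 14. Dividing instead gives 12 / 0.90 = 13.33, also 14. The 14 reproduces and is not in dispute.

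**Sections side by side.**
- Days 7, 14, 21 and 28 (10.5, 10.7, both halves): reapplication and oral hygiene review or instruction. No event or drug enquiry.
- Month 3 (10.5, 10.7): BoP, PPD, CAL, PI and GI. No event or drug enquiry.
- Recorded parameters (10.6): the same five.
- Analysis (Section 11): the same five, at two times. No safety row.
- Drugs (10.3): entry restriction only.

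The gap is consistent across all the operative sections that can be read.

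**Contacts without a required record.** 14 × 4 = 56 reapplication visits if all patients attend; 12 × 4 = 48 if 12 do.

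**Time after the last application.** Taking month 3 as day 90 (assumption): 90 − 28 = 62 days, and 62 / 90 = 69% of follow-up has no scheduled visit.

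**What a log could show.** The documents give no event rate, so per-patient rates of 5%, 10% and 20% are assumed. The chance that at least one of 14 patients has an event is 1 − (1 − p)^14:
- 5%: 1 − 0.95^14 = 51%
- 10%: 1 − 0.90^14 = 77%
- 20%: 1 − 0.80^14 = 96%

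If no patient has an event, the one-sided 95% upper limit is 1 − 0.05^(1/n):
- n = 14: 19.3%
- n = 12: 22.1%

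One patient in 14 is 7%, with an exact (Clopper-Pearson) 95% interval of 0.2% to 34%.

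These figures measure what the log could deliver, not the size of a bias. They support description and nothing more.

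**The case against.** **The extract is incomplete.** The flow chart in 10.9 has no content, consent pages were removed, and the Gantt chart lists a separate ethics application that was not seen. Any of these could carry a reporting duty, and the post-operative instructions might tell patients when to return. This stands: absence can be claimed only for the text available. None of it puts an item into 10.6 or a row into Section 11.

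**No planned conclusion depends on it.** All five specific objectives are between-half index comparisons. This also stands, and it limits the point to what the trial can report about tolerability.

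**Expected risk is low and some effects would show.** The product is recommended for oral intake, Section 9 cites earlier local use of probiotic drops, and entry requires HbA1c below 7%. Lasting local change would partly appear at month 3: oedema in the bleeding index, ulceration in the gingival index, and attachment loss in a chart whose acrylic stents serve "for pocket localisation to determine exact measurement sites in every visits". Routine clinic notes are neither required nor ruled out. What remains wholly missed is the transient event and the drug taken between visits.

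**A stronger reading to avoid.** Section 11 also tests "data within groups to evaluates statistically significant changes from baseline to follow up visits". A reader might infer that unrecorded antibiotics or anti-inflammatory drugs would bias those tests and so the efficacy result. The documents do not support this. Both halves receive debridement and repeated hygiene instruction, so a change within one half cannot isolate the drops with or without a drug log, and no objective is a within-half comparison. Systemic drugs also reach both halves of the same mouth, so they would tend to dilute the between-half contrast.

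**Conclusion.** The point holds for the text of 10.5, 10.6, 10.7 and Section 11. Following those sections as written, transient harms and post-baseline use of antibiotics, probiotics, NSAIDs or steroids would not be collected at up to 56 reapplication visits or at month 3. The trial could then report efficacy indices only, for a use it describes as unstudied in type 2 diabetes. The change should be made because it is cheap and the information may not be recoverable later. It is not a flaw in the effectiveness comparison.

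A reader might also infer that the trial has no safety oversight or that patients are being exposed to known harm. Neither follows: the consent and ethics documents were not seen, and nothing in the text indicates a high event rate.

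The verdict assumes that the unseen documents contain no event or medication log. The figure of 62 days also assumes that month 3 is day 90.

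**What to change.** In 10.5 and 10.7, add a one-page log completed before each reapplication (days 7, 14, 21, 28), and at month 3 after the indices are charted so that it cannot influence the charting. It should hold:
- by half: abscess, suppuration, swelling, pain, ulceration, tooth loss;
- per patient since the last visit: fever, unscheduled dental or medical care, and any antibiotic, probiotic, NSAID or steroid use.

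In Section 11, report local events by half, and systemic events and drug use by patient, descriptively with no test. Analyse all sites as randomised.

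**Cost.** 14 × 5 = 70 pages and a few minutes at visits that already exist. No extra visit or patient is needed.

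**Limits.** The operator who applies the drops knows the allocation, so entries at those visits are unblinded. Events after day 28 rely on recall over about 62 days. Systemic events cannot be assigned to a half. Precision is weak, as shown above.

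**Optional.** A rule for withholding a dose is a separate choice. It lets an unblinded operator alter exposure by half, each held dose removes 1 of 5 (20%) of that site's planned applications, and review by the periodontist may need extra attendance. If it is adopted, restrict it to prespecified objective signs, identical in both halves, and log every held dose with half and reason.

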10.8. Examiner Calibration

To ensure reliability of the parameter's measurements, intra and inter-examiner calibration will be done prior the study.

1. Intra-Examiner Calibration

[figure not shown]
The examiner ([name]) will assess the clinical parameters of five subjects in two separate sessions within 2 hours interval (Drucker et al., 2012; Polson, 1997). For periodontal pocket depth and clinical attachment level measurements, graduated UNC-15 probe with 1mm interval will be used. Only one quadrant will be assessed on each subject. Examiner will probe all six sites of each tooth in the chosen quadrant. Probing depth is measured in nearest mm between gingival margin up to the base of the pocket, while clinical attachment level is measured between the cemento-enamel junction (CEJ) to the base of the pocket. The accepted measurement difference was within $\pm 1\text{mm}$ (Hill et al., 2006). For bleeding on probing, plaque index, and gingival index; it will be recorded using Sulcus Bleeding Index (SBI) by Mühlemann & Son (1971), plaque index and gingival index by Löe (1967) accordingly, as stated above. Intra-examiner calibration is accepted when the intra-class correlation coefficient (ICC) value is ≥ 0.75 (Koo & Li, 2016) for each parameters.

2. Inter-Examiner Calibration

For this calibration, the supervisor, [name] [name], a periodontal specialist and an expert examiner will supervise and examine the inter-examiner agreement.

Three subjects (Polson, 1997) will be examined by both examiner ([name] and [name]) within 2 hours interval (Drucker et al., 2012; Polson, 1997). For periodontal pocket depth and clinical attachment level measurements, graduated UNC-15 probe with 1mm interval will be used. Examiners will probe all six sites of each tooth in the chosen quadrant. Probing depth is measured in nearest mm between gingival margin up to the base of the pocket, while clinical attachment level is measured between the cemento-enamel junction (CEJ) to the base of the pocket. The accepted measurement difference was within $\pm 1\text{mm}$ (Hill et al., 2006). For bleeding on probing, plaque index, and gingival index; it will be recorded using Sulcus Bleeding Index (SBI) by Mühlemann & Son (1971), plaque index and gingival index by Löe (1967) accordingly, as stated above. Inter-examiner calibration is accepted when the ICC value is ≥ 0.75 (Koo & Li, 2016) for each parameters.

10.9. Study Flow Chart

11. Statistical Analysis

All data will be collected in numerical form and will be analysed using the IBM SPSS Statistics Version 26.0 software. Histogram plot of data will be first used to check for normality of data distribution. Then, either Independent t-Test or Mann-Whitney Test will be used to compare data between two groups. The variables will be presented as mean and standard deviation for parametric test or median and interquartile range for non-parametric test. Significant level will be set at p-value $p < 0.05$. Meanwhile data within groups to evaluates statistically significant changes from baseline to follow up visits will be analysed either using Paired t-Test or Wilcoxon Signed Ranked Test.

Parameter	Visit	Control group	Test group	p-Value
BoP	Baseline			
	3 months			
PPD (mm)	Baseline			
	3 months			
CAL (mm)	Baseline			
	3 months			
PI	Baseline			
	3 months			
GI	Baseline			
	3 months			

Clinical Parameters for Groups 1 and 2 (mean \pm SD or median (IQR)) at different time intervals

(*denotes statistically significant difference, $p < 0.05$)

12. Budget

	Quantity	Cost/ Unit	Total Cost
Disposable syringe (1ml) (100's/ box)	1	RM 50.00	RM 50.00
Flexible tip (0.25mm) (100's/ box)	1	RM 200.00	RM 200.00
Gracey curettes	28	RM 209.25	RM 5859.00
Sharpening kit	1	RM 2442.00	RM 2442.00
Small cassette	3	RM 592.50	RM 1777.50
Lactobacillus reuteri probiotic	20	RM 134.50	RM 2690.00
Acrylic stents	20	RM 200.00	RM 4000.00
Oral hygiene kit	20	RM 100.00	RM 2000.00
		T O T A L COST	RM 19,018.50

13. Gantt Chart

	2023	2024				2025				2026			
	NOV- DEC	JAN- MAR	APR- JUN	JUL- SEP	OCT- DEC	JAN- MAR	APR- JUN	JUL- SEP	OCT- DEC	JAN- MAR	APR- JUN	JUL- SEP	OCT- DEC
Drafting proposal													
Defence of research proposal (DRP)													
Ethics application													
Data collection preparation													
Data collection													
Thesis write-up													
Submission research paper													
Thesis submission for viva													
Research sends for publication													

14. References

- Chandran, Arunah. (2020). National Diabetes Registry Report, 2013-2019. Ministry of Health Malaysia. https://www.moh.gov.my/moh/resources/Penerbitan/Rujukan/NCD/Diabetes/National_Diabetes_Registry_Report_2013-2019_26082021.pdf

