10.2. Sample Size Calculations

Sample size calculation done using G-power sample size calculator version 3.1.9.6 (Kang, 2021). The sample size calculation is based on the previous study by Minić and colleagues on the effect of the local probiotics in the therapy of periodontitis: a randomised prospective study (Minić, Pejčić, & Bradić-Vasić, 2022). The statistical test was set as “means: difference between two independent means (two groups)”, with an alpha error of 5%, and 90% statistical power. The minimum total sample size required is 12. Considering the probability of drop out rate 10%, 14 patients will be included.

$$\underline{12 + (12 \times 0.10) = 14}$$

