10.4. Study Design

This is a single blinded, prospective, randomised split-mouth clinical trial, where quadrants will be divided randomly into control and test groups.

Baseline records of periodontal clinical parameters will be taken for all subjects which include; bleeding on probing index (BoP), probing pocket depth (PPD), clinical

attachment level (CAL), plaque index (PI) and gingival index (GI). All the clinical records will be kept in locked case and delivered after the end of the clinical trial. University of North Carolina (UNC-15) probe will be used to measure the periodontal pocket depth and CAL.

All patients, after the baseline parameters recorded, will then receive motivation and oral hygiene instructions on standard effective oral hygiene practice which include tooth brushing, flossing, interdental brush usage and single tufted brush, followed by full mouth root surface debridement (RSD) under local anaesthesia on all teeth with pocket of ≥ 5 mm (Heitz-Mayfield, 2005; Matesanz-Pérez et al., 2013) using ultrasonic scaler and Gracey's curette, until the root surface feels smooth and clean to an explorer tip of UNC-15 probe (Kaner et al., 2007). For each patient, complete full mouth professional mechanical plaque removal (PMPR) and RSD will be done within 24 hours. All these will be done by main examiner, [name].

Both right (quadrant 1 and 4) and left (quadrant 2 and 3) halves will be assigned randomly to one of the two treatment modalities. A simple randomisation method will be employed to assign 14 participants into two groups (Group 1 and Group 2 corresponding to right halves: test and left halves: control or right halves: control and left halves: test) alternatively. A series of fourteen unique random numbers will be generated using the Numbers RAND() formula, one for each. Patients will then be alternately assigned to Group 1 and Group 2, starting with Group 1, done by supervisor, [name]. The treatment allocation cards will be sealed in envelopes until the clinical procedure.

The subgingival applications of either control (sterilised distilled water) or test (*Lactobacillus reuteri* probiotic) drops will be done based on the randomisation sequences done by [name] before. The allocated group for every subject will only be told to [name] on the

[figure not shown]

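### The split-mouth comparison of test and control halves is planned with an unpaired test, so its standard error, p-value and power are wrong

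*Combined protocol and SAP*

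**What the plan says.** Section 10.4 describes a "prospective, randomised split-mouth clinical trial" and states: "Both right (quadrant 1 and 4) and left (quadrant 2 and 3) halves will be assigned randomly to one of the two treatment modalities". Section 10.7 repeats this. Groups 1 and 2 there are the two side allocations (right half test and left half control, or the reverse), so each of the 14 patients contributes to both arms.

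Section 11 first says "Histogram plot of data will be first used to check for normality of data distribution" and then "Then, either Independent t-Test or Mann-Whitney Test will be used to compare data between two groups". Paired methods appear only for a different purpose: "Meanwhile data within groups to evaluates statistically significant changes from baseline to follow up visits will be analysed either using Paired t-Test" or the Wilcoxon signed-rank test. The results table in Section 11 sets a control column beside a test column with one p-value column, under a caption that begins "Clinical Parameters for Groups 1 and 2".

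Section 10.2 sizes the trial with the G*Power option for two independent means, at 5% alpha and 90% power. It arrives at 12 patients, raised to 14 for dropout. Nowhere do the documents provide a paired test, a mixed model or any other allowance for the pairing when test is compared with control.

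**The concern.** All five specific objectives in Section 6.2 ask how the test half compares with the control half at 3 months. That comparison is within patient: both halves share the same mouth, glycaemic control, oral hygiene, operator and examiner, so their values can be expected to be positively correlated. The independent t-test and the Mann-Whitney test take no account of this. They leave the differences between patients in the error term, although the design removes them.

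With a positive correlation and one value per half, the standard error and p-value are too large and the confidence interval is too wide. In a trial of 14 patients, a null result could then come from the choice of test.

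The normality check follows the same logic. A paired t-test depends on the distribution of the within-patient differences, and Section 11 does not say that these will be plotted. Choosing between tests from a histogram also leaves the decision until after the data are seen.

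**Working it through.** **Inputs from the documents.** Split-mouth, one test and one control half per patient (Sections 10.4, 10.7); unpaired between-group test (Section 11); alpha 5%, power 90%, 12 patients before dropout and 14 after (Section 10.2).

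**Assumptions.** Two-sided testing (sidedness is not stated); one normally distributed summary per half with equal variances; rho varied, because the documents give none. Below, d is the difference between halves divided by the between-patient SD of one half.

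**The plan's own figure.** The dropout step reproduces: 12 + 1.2 = 13.2, rounded up to 14. The 12 itself cannot be reproduced, because Section 10.2 gives no endpoint, effect or SD. Solving backwards for two independent groups at 90% power gives d = 2.08 with 6 per group and 2.35 with 5 per group, so a total of 12 implies d of roughly 2.1 to 2.3. That calculation sets 6 patients against 6 others, whereas the trial sets 12 halves against 12 halves of the same patients. Its 90% does not describe this design.

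**Standard error.** For n patients and common SD s:

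- correct (paired): s × sqrt(2(1 - rho)/n)
- planned (independent): s × sqrt(2/n)
- ratio: 1/sqrt(1 - rho), for example 1/sqrt(0.5) = 1.41

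**Effect for 90% paired power.** With 12 pairs, the paired t-test needs a mean difference of 1.03 SDs of the difference. Then d = 1.03 × sqrt(2(1 - rho)), which is 1.22 at rho 0.3, 1.03 at 0.5 and 0.80 at 0.7.

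**Simulation, 12 pairs, 100,000 trials per setting, two-sided 5%:**

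| rho | SE ratio | True type I error, planned t-test | Planned power where paired power is 90% | Power at fixed d = 0.8, planned vs paired |
|---|---|---|---|---|
| 0 | 1.00 | 5.0% | 92% | 47% vs 43% |
| 0.3 | 1.20 | 2.2% | 85% | 46% vs 57% |
| 0.5 | 1.41 | 0.9% | 73% | 46% vs 72% |
| 0.7 | 1.83 | 0.2% | 45% | 45% vs 90% |

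The paired t-test keeps about 5% type I error throughout. The Mann-Whitney test behaves like the planned t-test under the null: 2.0%, 0.9% and 0.2% at rho 0.3, 0.5 and 0.7. With 14 pairs, power at d = 0.8 (planned vs paired) is 54% vs 65%, 54% vs 79% and 56% vs 95%.

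**The case against.** The mismatch between design and test cannot be argued away. The objections concern its size and direction.

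- **The fall to 45% partly reflects a shrinking effect.** Holding paired power at 90% lowers d from 1.22 to 0.80 as rho rises. At a fixed d of 1.22, planned power is 85%, 88% and 92% at rho 0.3, 0.5 and 0.7, against 90%, 97% and nearly 100% for the paired test. This stands, and it is why the table also shows a fixed effect. At d = 0.8 the loss is 11, 26 and 45 points.
- **At the effect implied by N = 12 the loss vanishes.** At d = 2.08 with 12 pairs, both tests exceed 99% power. This stands too, but that effect is back-solved and the plan states no target.
- **The conservative direction needs one value per half per patient.** This stands. Section 10.6 defines the bleeding, plaque and gingival scores per individual over all teeth, and gives no aggregation rule for the six-site pocket depth and attachment readings. If sites were entered as separate records, the error could reverse. As an illustration, assume 30 sites per half, a patient share of 20% of the variance and a half-mouth share of 2% to 10%. The true variance of the difference is then about 30 × 0.02 + 0.78 = 1.38 to 30 × 0.10 + 0.70 = 3.70 times what the test assumes. Dividing 1.96 by the square roots of these (1.17 and 1.92) gives a type I error of about 10% to 31%.
- **The documents do not say why split-mouth was chosen.** True, and nothing here depends on the reason.
- **The plan does not say which data the histogram shows.** Also true. The check needs to be specified, and it follows from the choice of test.

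**Conclusion.** The point holds and must be fixed. The planned between-half test is invalid for this design and affects all five objectives.

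If each half gives one value and rho is positive, the error is conservative: it hides real differences and does not create false ones. Across rho 0.3 to 0.7 the standard error is 20% to 83% too large and the true type I error is 2.2% down to 0.2%. With 12 pairs and d = 0.8, power is 45% to 46% where a paired test would have 57% to 90%. At rho 0 the planned t-test would be slightly better, by about 2 points where paired power is 90%.

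These sizes rest on the assumed rho, normal data and two-sided testing. The need for a paired analysis rests on none of them.

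**What to change.** In Section 11, replace the between-group test as follows.

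1. For each parameter, compute one value per patient: the 3-month test-half summary minus the 3-month control-half summary.
2. Test the mean of these differences with a paired t-test and report it with its 95% confidence interval.
3. Name the Wilcoxon signed-rank test (or an exact sign-flip test) on the same differences as fallback or sensitivity analysis. Fix its role now, not from histograms of the raw data; any distribution plot should show the differences.

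Using within-patient differences in change from baseline, or a mixed model with a patient effect and baseline as covariate, would also respect the pairing. One primary form should be fixed in advance.

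Three texts should be brought into line. Section 10.6 should define the half-mouth summary for each parameter. The table caption should say control and test halves, because Groups 1 and 2 mean side allocations elsewhere. Section 10.2 should describe a matched-pairs calculation with its endpoint, effect, SD of the difference and sidedness.

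The cost is wording, plus redoing the short calculation in Section 10.2. Section 11 already names both the paired t-test and the signed-rank test, and SPSS provides them. No extra patients, visits or measurements are needed. The change is most credible if made before any outcome data are examined.
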